# **Statistical Analysis**

- 1. Preprocessing
  - Convert age from the NSQIP character variable to continuous variable, with Age "90+" recoded as 90
  - Standardizing the coding of missing values: missing coded in NSQIP as "-99", "unknown", "None Assigned", or "NULL". Each variable will be individually examined to ensure that the missing value is correctly standardized.
  - Pre-processing variables for survival analysis: creation of a censored 1 vs. 0 variable for each outcome to be modelled based on time-to-event and the occurrence of complications.
  - Missing values
    - Missing values for candidate predictors will be quantified. If the % missing is:
      - 1. >10% then exclude the predictor from the model
      - 2. <1% then delete (complete case analysis)
      - 3. >=1% and <10% then multiple imputation by chained equations (time-to-event variables are never imputed)
    - Note that patients with missing values for complications will be coded as zero for the complication (i.e. assumed to not have the complication), as the presence of complications would have been in the health records
    - The % missing data for height and weight will be examined in cohort characteristics. If <1% is missing, then BMI will be calculated using these variables.
    - Patients with a complication or adverse event but missing time-toevent data will be excluded from modeling. The extent of bias (i.e. if these patients have different cohort characteristics compared to patients without missing time-to-event data) will be assessed in sensitivity analysis. Note that it is expected for patients without a complication or adverse event to have missing time-to-event data, thus these patients are not excluded.
  - Check collinearity with variance inflation factor and Pearson's correlation coefficient: if present, combine information from collinear variables if feasible (e.g. new variables is "yes" if any of the variables it aggregates are "yes"), otherwise eliminate the variable that has more missing values or would be less accurately ascertained
  - Techniques for class imbalance: e.g. resampling within the derivation set to improve model performance in the case of rare outcomes
- 2. Descriptive statistics
  - Cohort characteristics will be stratified by mortality, by each complication and by derivation vs. validation sets (please see list below). Continuous variables will be presented as mean (standard deviation) and median (IQR) for parametric and nonparametric data, respectively. Categorical variables will be

4

presented as frequency (%). For comparison amongst groups, ANOVA will be used for parametric data, Kruskal-Wallis for nonparametric data, and Chisquare tests for categorical data. Standardized mean difference will be presented. Exploratory visualizations will be performed.

- Distribution of time to complication data (time to any complication, and time to each complication): failure curves, i.e. plotting the 1-S(t) (survival function) to determine the risk of complication daily within 30 days
- Exploratory analysis for complications that tend to occur concurrently or are associated with each other
- 3. Model building
  - Models will be created using the entire dataset and using bootstrap validation
    - Individual models will be built for each outcome.
    - Assumptions for the Cox model will be checked prior to model building, including but not limited to:
      - 1. Proportionality: visual inspection of the Kaplan-Meier curves, Log Log S(t) test, Schoenfeld residuals. If these assumptions hold, we will use the Cox proportional hazards (CPH) modeling; if not, we will use the accelerated failure time (AFT) modeling.
      - 2. Competing risk: complications are assumed to be independent from each other. If mortality is >10%, it will be modeled as a competing risk (however, we do not anticipate mortality to be >10% for elective colectomy).
    - Sensitivity analyses
      - 1. After examining the temporal distributions of events, we may include complications that tend to happen earlier as predictors for complications that happen later, and may be related to earlier complications
      - 2. For the two models to predict time-to-event for adverse outcomes (mortality and readmission), we will perform sensitivity analysis to determine whether including the occurrence of major complications (pneumonia, myocardial infarction (MI), cerebral vascular event (CVA), venous thromboembolism (VTE), acute renal failure (ARF), and sepsis) as predictors improve discrimination and calibration
      - 3. Restricted cubic splines for continuous predictors (age, BMI, duration of surgery) to explore non-linear relationships
      - 4. Compare cohort characteristics for patients with a complication or adverse event but missing time-to-event data, vs. patients without missing time-to-event data, to evaluate for the impact of bias from the exclusion of patients with missing time-toevent data
    - Additional analysis will be performed to improve time-to-event predictions, including but limited to:
      - 1. Accelerated failure time (AFT) modeling to directly model failure time. Compared to CPH, APT is more interpretable and robust with omitted predictor variables.
      - 2. Machine learning models that can facilitate time-to-event predictions: including but not limited to boosting trees, neural networks.
- 4. Model evaluation, with bootstrapped 95% confidence intervals and optimism

 Nov 9, 2021
 Protocol Version #2
 Ke et al.
 REB# H21-02670
 5

- AUROC, pseudo R-squared, scaled Brier, calibration plots
- 5. Sample size calculation
  - We used the PMSampsize package in R and followed guidance specifically for time-to-event multivariable modeling (6). Based on an event rate of 0.01 over 30 days (i.e. 0.00033333 per patient per day in the study period totalling 30 days), Cox-Snell R-squared 0.11 (the maximum for the event rate of 0.01 over 30 days) (6), 0.05 acceptable difference in apparent & adjusted R-squared, shrinkage 0.9, a minimum of 51 events (5091 patients, 15,2730 person-days of follow-up) are required for modeling with 30 predictor variables.

Data will be analyzed using R and/or Python.

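### Dropping patients whose known event has no recorded day, while keeping event-free patients, lowers that outcome's modeled 30-day risk by roughly the undated share in relative terms, and no planned check measures this

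*Combined protocol and SAP*

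**What the plan says.** The rule is in the Statistical Analysis section, item 1 (Preprocessing), under missing values: "Patients with a complication or adverse event but missing time-toevent data will be excluded from modeling". Patients without the event also have no event time. The plan expects this, and "thus these patients are not excluded". The rule on chained-equation imputation adds that "time-to-event variables are never imputed".

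The plan recognizes that the exclusion may cause bias. Its response, given in the same bullet and again as item 4 of the sensitivity analyses under Model building, is to compare the cohort characteristics of patients with and without a missing event time. No planned analysis puts the undated events back.

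Three other provisions matter here:

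- Each outcome gets its own model. On validation, item 3 says "Models will be created using the entire dataset and using bootstrap validation", and item 4 (Model evaluation) lists calibration plots. Objective 2 names calibration as a basis for comparing models.
- Descriptive statistics include event frequencies, and failure curves "to determine the risk of complication daily within 30 days".
- The plan sets percentage thresholds for missing candidate predictors but none for missing event days. It does not say how many events lack a day. It also does not say whether a patient with one undated event leaves that outcome's model only or every model.

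**The concern.** Only a patient known to have had the event can be removed by this rule. A patient without the event cannot be. The numerator of the risk therefore loses a share of its events, while the denominator loses almost nothing. This is selection on the outcome, and it lowers absolute risk even if undated and dated patients are alike in every recorded characteristic. A reassuring comparison of characteristics would say nothing about it.

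The models are meant to predict whether and when a complication occurs, and they will be judged partly on calibration. Bootstrap validation resamples the same depleted data, so predicted and observed risk would be low together and would agree. If m is appreciable, the published absolute risks would be too low by an amount that no planned output reveals directly.

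**Working it through.** **Inputs.** From the documents: p = 0.01 over 30 days (Sample size calculation), about 130,000 patients (Study Population), eight outcomes (six complications, mortality, readmission). Assumed, because the documents give no figure: m = 1%, 5% and 10%; p = 10% for a commoner outcome; exclusion applied per outcome.

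**The plan's own figure.** The sample-size item is used here only for p. Its parts agree with one another: 5091 × 0.01 = 50.9 events and 5091 × 30 = 152,730 person-days. With R-squared and its maximum both at the rounded 0.11, S = 0.11/(0.11 + 0.05 × 0.11) = 0.9524, and 30/[(S − 1) ln(1 − 0.11/S)] gives 5134 patients, within 0.8% of 5091. Nothing below depends on that total.

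**Effect of the rule.** Of N patients, Np have the event. Removing Npm of them leaves Np(1 − m) events among N(1 − pm) patients:

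- modeled average risk = p(1 − m)/(1 − pm)
- relative fall = m(1 − p)/(1 − pm)
- observed/expected if undated events are counted = (1 − pm)/(1 − m)

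At p = 1%, with 1,300 events expected in 130,000 patients:

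| m | events dropped | modeled risk | fall, percentage points | observed/expected |
|---|---|---|---|---|
| 0 | 0 | 1.000% | 0 | 1.000 |
| 1% | 13 | 0.990% | 0.010 | 1.010 |
| 5% | 65 | 0.950% | 0.050 | 1.052 |
| 10% | 130 | 0.901% | 0.099 | 1.110 |

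At the assumed p = 10%, the same values of m give 9.91%, 9.55% and 9.09%. The relative fall at m = 10% is 9.1%, or 0.91m.

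**Against sampling error.** The 95% half-width at p = 1% is 1.96 × √(0.01 × 0.99/130,000) = 0.054 point. The falls are therefore 0.18, 0.92 and 1.83 half-widths. The fall equals one half-width at m = 5.5%. At p = 10% the half-width is 0.163 point, and the crossing is at m = 1.8%. This is a statistical yardstick, not a clinical one.

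**Simulation of the fitted model (assumed inputs).** The setting was 130,000 patients, about 1% risk, two binary predictors, early-skewed event days, 0.5% censored at death, days missing completely at random, a Cox model and 20 runs.

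| m | complete data | exclusion | day multiply imputed |
|---|---|---|---|
| 1% | 0.9915% | 0.9816% | 0.9915% |
| 5% | 1.0040% | 0.9530% | 1.0040% |
| 10% | 0.9977% | 0.8996% | 0.9977% |

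For the exclusion model, observed/expected on the retained patients was 1.000 at each m. Bootstrap refits gave 1.000, 1.005 and 1.006. With undated events counted it was 1.011, 1.054 and 1.109. At m = 10% a hazard ratio of 2.0 was estimated as 2.008 with complete data and 2.007 with exclusion, so the loss is in the baseline risk. At the same m, placing every undated event at day 0 or at the last possible day gave 0.9975% and 0.9981%, so the 30-day total hardly depends on the imputed day.

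**When missingness depends on a predictor.** In a smaller simulation (40,000 patients, one predictor, single runs), average risk fell by 11.0% for realized m = 11.2% at p near 1%, and by 8.1% for m = 10.0% at p near 10%. The log hazard ratio in the first of these also shrank, from 0.63 to 0.54. The planned comparison of characteristics could point to this second problem. It cannot measure the first.

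**The case against.** The strongest reply is that m may be close to zero. Methods describes a prospectively collected dataset that records days to diagnosis under standardized criteria, and nothing in the documents suggests that 5% or 10% of events lack a day. This stands: the size is wholly conditional on m.

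Second, the plan discloses the exclusion, calls it a possible source of bias and reports event frequencies. The comparison of patients with and without event times would ordinarily show group sizes, from which a reader could approximate m. This stands in part. Reporting m by outcome is not promised, and the check as defined looks at characteristics, not risk.

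Third, not imputing event days is defensible when timing is the target. This also stands. The robustness shown above is for the 30-day total, not for predicted timing, and imputing within every bootstrapped Cox, accelerated failure time and machine learning model has not been shown to be cheap.

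A reader might also infer more than the documents support:

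- *That risk falls by m percentage points.* The fall is relative. At p = 1% and m = 10% it is 0.099 point.
- *That final predictions will be too low overall.* Other steps also move net risk. Possible "resampling within the derivation set to improve model performance in the case of rare outcomes" would probably raise it, as would treating death as censoring under the rule "If mortality is >10%, it will be modeled as a competing risk". Coding missing complications as absent can only lower it. If resampling is used, calibration on the retained patients need not look clean either.
- *That the failure curves are biased.* They are only if the exclusion is applied to them, and the plan speaks of exclusion from modeling.
- *That the plan already sets a 1% tolerance for m.* Its rule "<1% then delete (complete case analysis" concerns predictors missing among patients. At p = 1%, m = 1% is 13 of 130,000 patients, or 0.01%.

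**Conclusion.** The concern holds as a statement about this rule taken alone. It lowers an outcome's modeled average 30-day risk to p(1 − m)/(1 − pm), a relative fall of about m at p = 1% and of about 0.91m at p = 10% with m = 10%. It has no effect at m = 0 and is negligible below about 1%. Neither the planned comparison of characteristics nor calibration on the retained patients measures it.

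The formula assumes exclusion outcome by outcome. If a patient with any undated event leaves every model, each outcome still loses its own undated events, but the formula is no longer exact. With days missing at random, hazard ratios are essentially unchanged. Because m is unknown and the net direction of all planned steps is not established, the point is minor. It is worth acting on because the plan sets out to assess this bias and uses a check that cannot see it.

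**What to change.** 1. State whether the exclusion is per outcome or across all models, and report m, with numerator and denominator, for each of the eight outcomes.
2. Extend sensitivity analysis 4. For the main model, also predict for the excluded patients, and report average 30-day risk and calibration-in-the-large with undated events counted as observed. This needs event status by day 30, not the day.
3. Where m is not negligible, add one sensitivity analysis of the main Cox or accelerated failure time model that keeps these patients as events. A trigger of 1% of events would serve. It is a chosen value, and it lies below both half-width crossings. Either multiply impute the day within days 0 to 30, bounded by death or last follow-up where known and conditional on predictors and observed event days, or treat the day as interval-censored. Amend the ban on imputing event times to allow this, for known events in that analysis only.

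**Cost.** No new data, a few sentences in the plan, and modest extra analysis confined to the main model for outcomes that reach the trigger. Step 3 assumes that the day is missing at random among events. This hardly affects 30-day risk but can affect predicted timing, so the dated-event analysis can stay primary for timing.

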# Development and internal validation of models to predict time-to-event for major medical complications within 30-days after planned colectomy: a retrospective population cohort study

# Introduction

Planned (elective or time sensitive) colectomy are performed for indications including cancer, inflammatory bowel disease (IBD), and diverticulitis (1,2). After colectomy, patients are at risk of a variety of major medical complications, including pneumonia, myocardial infarction (MI), cerebral vascular event (CVA), venous thromboembolism (VTE), acute renal failure (ARF), and sepsis (2,3). However, different complications tend to happen at different times after surgery. Accurate risk prediction, not only whether a complication may occur in a patient, but also when, is crucial for patient education, monitoring, and disposition planning. While several studies have explored the incidence and binary risk prediction for major complications after surgeries (1–3), there has been scarce literature on time-to-complication prediction modeling in recent population cohort data.

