# Objectives

- Develop and internal validate Cox proportional hazards models to predict time-tocomplication for each individual major medical complication captured in the American College of Surgeons National Surgical Quality Improvement Program (NSQIP) dataset (pneumonia, myocardial infarction (MI), cerebral vascular event (CVA), venous thromboembolism (VTE), acute renal failure (ARF), and sepsis) or adverse outcomes (mortality, readmission), that started within 30-days after elective colectomy.
- 2. Develop and internal validate machine learning models to predict time-tocomplication for major medical complications and adverse outcomes (same as in objective 1) within 30-days after elective colectomy in NSQIP. The best machine learning model for each complication will be compared to the Cox proportional hazards model in terms of discrimination, and calibration.

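### If used, the optional outcome resampling for rare complications would inflate predicted 30-day risks, and the plan has no step that brings them back to the true event rate

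*Combined protocol and SAP*

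**What the plan says.** The class-imbalance provision is the last item under Statistical Analysis, 1. Preprocessing: "Techniques for class imbalance: e.g. resampling within the derivation set to improve model performance in the case of rare outcomes". It is offered as an example. No ratio, method (under- or oversampling), rarity threshold or model type is given.

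Item 3, Model building, states: "Models will be created using the entire dataset and using bootstrap validation". Item 2, Descriptive statistics, nevertheless stratifies the cohort tables "by each complication and by derivation vs. validation sets". No such split is defined anywhere.

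Item 4 lists the performance measures: "AUROC, pseudo R-squared, scaled Brier, calibration plots", with bootstrap confidence intervals and optimism. Objective 2 says the best machine-learning model for each complication "will be compared to the Cox proportional hazards model in terms of discrimination, and calibration". The document contains no recalibration, no re-estimation of the baseline hazard, no sampling weights and no prevalence correction.

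**The concern.** Keeping or duplicating patients according to their outcome changes the proportion of events in the training data. A model fitted to those data reproduces the altered proportion. In a Cox model the shift enters mainly through the baseline hazard; in boosted trees or a neural network it enters the predictions directly. Ranking, and hence AUROC, is largely unaffected, so a team that looks first at discrimination may not notice.

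Two things are at stake.

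- **Absolute risk.** The Introduction says that accurate prediction of whether and when a complication occurs "is crucial for patient education, monitoring, and disposition planning". Those uses need correct absolute risks as well as correct ranking.
- **The comparison in Objective 2.** If resampling is applied to some models and not others, a difference in calibration partly reflects the resampling and not the learner.

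The undefined derivation set adds to the problem. When models are built on the whole dataset with bootstrap validation, the term does not show whether resampling precedes the bootstrap, happens inside each replicate, or also reaches the data used for testing.

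**Working it through.** **Inputs from the plan.** About 130,000 patients (Study Population); 30 predictors and a 1% event rate (Sample size calculation: "Based on an event rate of 0.01 over 30 days").

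**Assumptions.** The plan gives no resampling ratio, so I took events doubled and event shares of 10%, 20% and 50% (1:1). The standard deviation of the log hazard across patients is set at 0.8. True rates of 0.5% and 3% give the range.

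**The plan's own figure.** The sample-size formula is n = P / [(S − 1) ln(1 − R²/S)]. With P = 30, R² = 0.11 and S = 0.11/(0.11 + 0.05 × 0.11) = 0.9524, n is 5,134. Rounding S to 0.952 gives the plan's 5,091. Then 5,091 × 0.01 = 50.9, or 51 events, and 5,091 × 30 = 152,730 person-days. The figure reproduces. The cohort would supply about 130,000 × 0.01 = 1,300 events at that rate, against that minimum of 51, so rarity alone is a weak reason to resample.

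**Step 1: size of the shift.** Moving the event share from p to q multiplies each patient's odds by

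k = [q/(1 − q)] / [p/(1 − p)].

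For p = 0.01 and q = 0.10, k = 0.1111/0.0101 = 11.0. A patient with a true risk of 1% is then told 10%. For q = 0.20 and 0.50, k = 24.75 and 99.

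**Step 2: average over patients.** The table applies k across the assumed risk distribution and sets the result beside a fitted Cox model. The fitted figures come from a simulation with 130,000 development patients, 200,000 unresampled test patients, 30 predictors, six replicates and a Breslow baseline. Each ratio is mean predicted risk divided by true or observed risk.

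| Training data | Ratio, identity | Ratio, fitted Cox | Scaled Brier, identity | Scaled Brier, fitted Cox |
|---|---|---|---|---|
| Not resampled | 1.0 | 0.98 | 0.009 | 0.008 |
| Events doubled | 1.96 | 1.9 | −0.008 | −0.007 |
| 10% events | 9.4 | 9.4 | −1.09 | −1.1 |
| 20% events | 18.1 | 18 | −4.05 | −4.0 |
| 1:1 | 43.1 | 43 | −20.7 | −20 |

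With true rates of 0.5% and 3%, Cox inflation is 19-fold and 3.2-fold at a 10% share, and 86-fold and 14-fold at 1:1.

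**Step 3: a second Cox simulation.** Two predictors and an observed risk of 0.94% gave inflation of 9.0, 19.0 and 45.7 at event to non-event ratios of 1:10, 1:4 and 1:1. AUROC stayed at 0.718. The 30-day baseline cumulative hazard rose from 0.0068 to 0.0702 at 1:10 and 0.5391 at 1:1.

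**Step 4: other learners, first simulation.** Boosted trees and a one-layer, 16-unit network overstated mean risk 1.9 to 2.0, 9.2 to 9.5 and 42 to 45 times for events doubled, a 10% share and 1:1. AUROC without and with resampling:

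- Cox: 0.708 against 0.702 to 0.708
- boosted trees: 0.696 against 0.688 to 0.696
- untuned network: 0.673 against 0.684 to 0.697

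**Step 5: is resetting the baseline enough?** It restores the mean but not the spread. In the second simulation the log hazard ratios at 1:1 were 0.38 and 0.30, against 0.64 and 0.53 without resampling. In the first, a Cox model at 1:1 with only its baseline reset had a calibration slope of 1.49 to 1.55 and a scaled Brier of 0.006. Correcting level and slope gave a slope of 0.99 and a scaled Brier of 0.008. For the other learners at 1:1 the choice of recalibration patients matters. Level and slope fitted on training patients left slopes of 0.62 to 0.72 (trees) and 0.76 to 0.90 (network). Fitted on unresampled patients not used for training, they gave 1.00 to 1.02 and 1.01 to 1.04.

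**The case against.** Resampling is only an example and no model is committed to it. Every multiple above depends on a ratio I chose, and the 1% rate is a design input, not an observed rate for any of the eight outcomes. This stands: the documents fix the direction of the error but not its size.

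Confining resampling to a derivation set most naturally means that testing uses untouched patients. The plan's own measures would then expose a large error, since a scaled Brier of −1.1 or worse could hardly pass for improved performance. That reading of the intent is fair. It still leaves the risks uncorrected, because a calibration plot detects miscalibration without removing it, and optimism correction addresses overfitting, not a shifted event rate. Mild resampling is also harder to see: doubling events moves scaled Brier only from 0.008 to −0.007 while nearly doubling the stated risks.

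The clinical uses appear only in the Introduction, and the objectives stop at internal validation. True, but calibration is itself a stated comparison criterion, so the matter bears on the study's own results.

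Finally, deletion may look too strong when the simulated network gained 0.020 to 0.024 in AUROC at 1:1. That network was small and untuned, and its results and those for boosted trees come from one simulation set-up. The gain is a reason to offer a safeguarded alternative, not to leave the step as it is.

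**Conclusion.** The concern holds in its conditional form. If the resampling option is used as written, predicted 30-day risks will be too high by an amount set by an unspecified ratio, and no later step corrects them. At a 1% event rate and a log-hazard standard deviation of 0.8, the Cox overstatement runs from about 1.9-fold (events doubled) to 43-fold (1:1). Resampling brought no AUROC gain for Cox or boosted trees. The mechanism is certain; whether it occurs in this study, and how large it is, depend on choices the plan leaves open. It should be fixed before analysis.

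**What to change.** Delete the class-imbalance resampling step and fit all models at the observed event rate, with penalisation if wanted.

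If a particular learner, such as a neural network, is still to be trained on resampled data, the SAP should:

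1. state the ratio, the method and the outcomes and models concerned;
2. resample only inside each bootstrap replicate;
3. recalibrate both level and slope on unresampled patients of that replicate who were not used to train the learner, for example with folds split by patient so that bootstrap copies stay together;
4. compute calibration, Brier and AUROC on unresampled patients only;
5. say what follows if miscalibration is seen.

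In either case, bring the references to derivation and validation sets into line with the whole-dataset bootstrap design.

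Deletion costs only SAP wording. Its possible downside is an AUROC 0.01 to 0.02 lower for a network like the untuned one simulated; Cox and boosted trees lost nothing. Keeping resampling for a learner adds one recalibration step per replicate.

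### Scoring machine learning against Cox by bootstrap optimism can reward the most overfit learner and report a false gain over Cox

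*Combined protocol and SAP*

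**What the plan says.** All references are to the combined protocol and SAP.

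- Objectives, objective 2: "The best machine learning model for each complication will be compared to the Cox proportional hazards model in terms of discrimination, and calibration".
- Statistical Analysis, item 3 (Model building): "Models will be created using the entire dataset and using bootstrap validation".
- Same item, additional analysis, with an open list of learners: "Machine learning models that can facilitate time-to-event predictions: including but not limited to boosting trees, neural networks".
- Statistical Analysis, item 4: "Model evaluation, with bootstrapped 95% confidence intervals and optimism", applied to "AUROC, pseudo R-squared, scaled Brier, calibration plots". This one line covers Cox, AFT and machine learning alike.

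The plan does not name the bootstrap variant, describe any tuning, say whether tuning and selection are repeated inside each resample, or give the rule that makes a model the best one.

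Two other places hint at a data split that is never defined. Item 2 (Descriptive statistics) tabulates the cohort "by each complication and by derivation vs. validation sets", which conflicts with building on the whole dataset. Item 1 (Preprocessing) allows "resampling within the derivation set to improve model performance in the case of rare outcomes"; this may mean each bootstrap training sample, but the plan does not say so.

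**The concern.** Optimism correction ordinarily means apparent performance minus the average optimism, where each bootstrap model is tested on the full original cohort. Most of those test patients were also training patients. A regression with 30 predictors hardly memorises individuals, so little is lost. A deep boosted ensemble does memorise them, scores well on the patients it has already seen, and so has its optimism underestimated. The bias falls on one side of the comparison only.

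Two consequences follow. A single overfit learner can appear to beat Cox when it is worse. And if the best model is chosen by corrected score, which the plan neither states nor excludes, the choice leans towards the most overfit candidate. Objective 2 is one of two stated objectives and is repeated for eight outcomes.

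**Working it through.** **Inputs from the plan.** About 130,000 patients (Study Population); event rate 0.01 over 30 days and 30 predictors (item 5, Sample size calculation). Expected events: 130,000 × 0.01 = 1,300.

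**The plan's own figure.** The plan gives no figure for this comparison. Its sample size does reproduce: n = P / [(S − 1) ln(1 − R²/S)] with P = 30, R² = 0.11 and S = 0.11/(0.11 + 0.05 × 0.11) = 0.952 (rounded) gives 5,091 patients, and 5,091 × 0.01 ≈ 51 events. That calculation is for a regression with 30 predictors and does not address overfitting by a flexible learner.

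**Overlap.** The chance that a patient enters a bootstrap sample of size n is 1 − (1 − 1/n)ⁿ ≈ 1 − e⁻¹ = 0.632.

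**Main simulation (assumed).** Exponential event times in whole days, censored at day 30; 3 continuous and 27 binary predictors; 10 bootstraps per cohort; true performance measured in 200,000 new patients. There was one cohort for each of three truths: linear, mildly non-linear and strongly non-linear (1,299 / 1,316 / 1,325 events; best possible AUROC 0.698 / 0.712 / 0.818). The non-linear truths are relevant because the plan itself foresees "Restricted cubic splines for continuous predictors (age, BMI, duration of surgery) to explore non-linear relationships". Cox had linear terms. Boosting used a Cox loss at four settings (depth / rate / rounds): light 2 / 0.1 / 100; depth 3, 3 / 0.05 / 200; medium 4 / 0.1 / 200; library default 6 / 0.3 / 100.

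| Truth | Model | Corrected AUROC | Out-of-bag | 5-fold | True | Minus Cox, corrected | Minus Cox, true |
|---|---|---|---|---|---|---|---|
| Linear | Cox | 0.684 | 0.677 | 0.681 | 0.694 | | |
| | Light | 0.680 | 0.664 | 0.672 | 0.684 | −0.005 | −0.010 |
| | Depth 3 | 0.689 | 0.658 | 0.670 | 0.680 | +0.005 | −0.014 |
| | Medium | 0.734 | 0.631 | 0.648 | 0.668 | +0.049 | −0.027 |
| | Default | 0.812 | 0.589 | 0.605 | 0.633 | +0.128 | −0.061 |
| Mild | Cox | 0.663 | 0.656 | 0.660 | 0.686 | | |
| | Light | 0.682 | 0.670 | 0.674 | 0.695 | +0.020 | +0.009 |
| | Depth 3 | 0.691 | 0.666 | 0.671 | 0.693 | +0.028 | +0.007 |
| | Medium | 0.735 | 0.641 | 0.653 | 0.675 | +0.072 | −0.011 |
| | Default | 0.819 | 0.591 | 0.605 | 0.625 | +0.156 | −0.061 |
| Strong | Cox | 0.695 | 0.693 | 0.694 | 0.710 | | |
| | Light | 0.793 | 0.783 | 0.789 | 0.798 | +0.098 | +0.088 |
| | Depth 3 | 0.797 | 0.784 | 0.790 | 0.803 | +0.102 | +0.093 |
| | Medium | 0.821 | 0.772 | 0.782 | 0.798 | +0.126 | +0.088 |
| | Default | 0.893 | 0.699 | 0.729 | 0.740 | +0.198 | +0.030 |

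Some differences were taken before rounding and differ by 0.001 from the displayed values.

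**Order against Cox.** Corrected AUROC was wrong in 5 of 12 comparisons, corrected pseudo R-squared (McFadden form assumed) in 4 and corrected scaled Brier in 3. Five-fold cross-validation was right in 12 of 12 on all three measures. On AUROC, out-of-bag scoring was right in 12 of 12, .632+ in 10 and plain .632 in 7.

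**Selection.** Corrected AUROC picked the default setting under every truth. The loss against the truly best candidate was 0.684 − 0.633 = 0.051, 0.695 − 0.625 = 0.070 and 0.803 − 0.740 = 0.063. Five-fold cross-validation picked the truly best candidate each time.

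**Calibration slope, corrected against true.** Cox 0.95 to 0.97 against 1.03 to 1.10; medium 1.12 against 0.73, 1.08 against 0.78 and 0.93 against 0.91; default 1.00 to 1.03 against 0.36 to 0.57. The calibration check would therefore not expose the default model.

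**Further linear cohorts.** In three more, the default setting minus Cox was +0.107 to +0.111 corrected against −0.076 to −0.064 true. One neural network was overstated (0.725 against 0.654) but did not overtake Cox (0.729).

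**Checks with logistic regression standing in for Cox**, at 130,000 patients, corrected / true AUROC:
- 1,305 events, 3 bootstraps: regression 0.687 / 0.688; shallow boosting 0.679 / 0.678; default boosting 0.805 / 0.652; fully grown random forest 0.890 / 0.599.
- 1,333 events, 4 bootstraps: regression 0.719 / 0.734; light 0.715 / 0.722; default 0.828 / 0.699; deeper 0.813 / 0.665. The top-scored model was second worst here, not worst.
- 1,306 events, 4 bootstraps: regression 0.749 / 0.745; depth 2 0.753 / 0.739; depth 4 0.786 / 0.729; default 0.854 / 0.689. Here even light boosting was slightly reversed against regression.

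**The case against.** The strongest reply is that the fault needs three things the plan does not state: that optimism means ordinary subtraction, that a heavily flexible or untuned learner is among the candidates, and that the best model is chosen by corrected score. With sensible learners the ordering mostly held. In the main simulation light boosting was ranked correctly under all three truths, and the candidate picked by cross-validation was ranked correctly even when scored by optimism. Four of the five AUROC reversals came from medium or default settings; the fifth was a corrected lead of only 0.005. The selection result is for AUROC alone, whereas the plan lists several measures, and under the linear truth corrected scaled Brier penalised medium boosting (−0.024 against a true 0.002). The plan lists calibration plots, not the slope. Replicates are few.

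Much of this stands as a limit on scope: the claim is about what can happen, not what must. It does not remove the concern. Ordinary subtraction is the normal meaning of the word the plan uses, and nothing in the plan commits to tuning or to scoring on left-out patients. The failing settings include off-the-shelf defaults. A default model reverses the comparison under two of the three truths with no selection step at all. Reading several measures together helps only in part: default boosting was misordered on pseudo R-squared under all three truths and on scaled Brier under both non-linear ones. The derivation and validation wording is a separate drafting matter and adds nothing to the overfitting argument.

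**Conclusion.** The concern holds, conditionally. As written, the plan can name an overfit learner as best, show it as well calibrated and report a false or inflated gain over Cox. At the planned size, corrected minus true AUROC in the main simulation was +0.153 to +0.194 for default boosting and +0.023 to +0.066 for medium. It was −0.013 to −0.005 for light boosting and −0.023 to −0.010 for Cox.

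This assumes ordinary optimism subtraction, a 1% event rate and the simulated truths described, with one cohort per non-linear truth. Single-model figures carry sampling noise, which largely cancels in the differences from Cox. In the three further linear cohorts, early-stopped boosting showed no material reversal, but those fits were disturbed by copies of one patient falling on both sides of the stopping split. AFT models, imputation, class resampling, confidence intervals and other event rates under non-linear truths were not tested. Confidence is medium. The point should be fixed before analysis; it does not invalidate the study.

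**What to change.** 1. In Statistical Analysis items 3 and 4, for the comparison with Cox, replace optimism correction by scoring all models on the same patients left out of each fit, using cross-validation with tuning nested inside. With 5 outer and 3 inner folds, this reported machine learning minus Cox AUROC of −0.009 / +0.015 / +0.096 against true differences of −0.010 / +0.009 / +0.093. Out-of-bag scoring is an acceptable alternative if tuning and early-stopping folds are split by patient. Plain .632 should not be used. Optimism correction can stay for Cox reported on its own.
2. Carry out imputation, class resampling, tuning and the choice of the best model inside each training sample, and state the selection rule in advance.
3. Report the paired machine-learning-minus-Cox difference with its confidence interval, for AUROC and for calibration.
4. Reconcile the cohort table by derivation and validation set with the use of the whole dataset, and define the derivation set named in Preprocessing.

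The cost is SAP wording and computing time; no new data are needed. Out-of-bag scoring is slightly pessimistic, because each fit sees only about 63% of distinct patients, and it can misorder models that are close.
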